9.3 Study Restrictions

Study restrictions related to the biomarker assessments are summarized in Table 9-1.

Table 9-1 Study Restrictions

Restricted Medication/Food/Activity ^a	Timing of Restriction
MCC	
No hypertonic saline, bronchodilator, or dornase alfa usage	12 hours before MCC procedures
WMC	
Food or drink (water permitted)	8 hours before WMC administration AND for 4 hours immediately after WMC administration with a snack bar
Proton-pump inhibitors ^b	1 week before WMC administration until capsule has passed
Calcium, aluminum, or magnesium antacids ^b	24 hours before WMC administration until capsule has passed
Histamine 2 blockers ^b	48 hours before WMC administration until capsule has passed
Narcotic medications ^b	48 hours before WMC administration until capsule has passed
Chronic laxatives changes	From Screening until the last WMC has passed
Tobacco	8 hours before WMC administration and for 6 hours immediately after WMC administration
Alcohol	24 hours before WMC administration until capsule has passed
Rigorous exercise	From WMC administration until capsule has passed
MRI	No MRI from patency capsule or WMC administration until capsule has passed

MCC: mucociliary clearance; MRI: magnetic resonance imaging; WMC: wireless motility capsule

^a See [Section 9.4](#) for guidance for concomitant medications.

^b A nonexhaustive list of medications is included in the Study Reference Manual. For questions, contact the Vertex medical monitor.

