^d Subjects will be offered the option of an overnight stay in proximity to the clinic between Days 28 and 29.

^e A telephone contact will occur on Day 14 to review adverse events (AEs) and concomitant medications.

^f Confirmation of subject eligibility will occur before randomization.

^g Weight and height will be measured before dosing with shoes off. Height will be collected only for subjects 21 years of age or younger at the Day 1, Day 28, and Safety Follow-up Visits.

^h A complete physical examination will occur on Day 1 and at the Safety Follow-up Visit. Symptom-targeted physical examinations will occur at any time during the study if triggered by AEs or if deemed necessary by the investigator.

ⁱ All ECGs will be performed before vital signs, pulse oximetry, and any other procedures that may affect heart rate (e.g., blood sampling). Subjects must be supine for at least 5 minutes before the start of the ECG.

^j At the Day 1 and Day 29 Visits, ECGs will be collected before dosing and at 1.5 (approximately ± 15 minutes) and 3 hours (approximately ± 15 minutes) after the morning dose of study drug. ECGs collected on Day 1 before dosing will be performed in triplicate. If study drug is not administered on the Day of the visit (i.e., because of study drug interruption or permanent discontinuation of study drug), only 1 ECG will be collected.

^k Vital signs and pulse oximetry will be collected before dosing and after the subject has been at rest (seated or supine) for at least 5 minutes. Vital signs will be performed after ECGs and before blood sampling. In cases where Day 28 Visit assessments occur on 2 separate days, vital signs and pulse oximetry will be collected on both days.

^l Spirometry will be performed before study drug dosing and should be performed prebronchodilator (see [Section 11.4.1](#)). At the Day 28 Visit, bronchodilator usage is restricted for 12 hours before the MCC assessment. If the Day 28 Visit assessments occur on 2 separate days, spirometry should be performed on the same day as and preceding the MCC assessment.

Table 3-2 Study VX14-661-111: Treatment Period and Safety Follow-Up Visit

Event/Assessment ^a	Treatment Period				Telephone Contact 5 Days After WMC Administration	Early Treatment Termination ^b Visit	Safety Follow-up Visit 28 (± 7) Days After Last Dose of Study Drug
	Day 1	Day 14 (± 3 days)	Day 28 (± 3 days) ^c	Day 29 (± 3 days)			
Urinalysis	X			X		X	X
Sweat chloride ⁿ	X			X			

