11.4 Key Efficacy Assessments

11.4.1 Spirometry

Spirometry will be performed according to the American Thoracic Society Guidelines²³ at the time points noted in [Table 3-1](#) and [Table 3-2](#) according to the additional guidelines that follow.

Prebronchodilator spirometry is defined as spirometry testing performed for subjects who have:

- withheld their short-acting bronchodilators (e.g., albuterol) or anticholinergic (e.g., Atrovent) for more than 4 hours before the spirometry assessment;
- withheld their long-acting bronchodilator (e.g., salmeterol) for more than 12 hours before the spirometry assessment; and
- withheld their once-daily, long-acting bronchodilator (e.g., tiotropium bromide [Spiriva®]) for more than 24 hours before the spirometry assessment.

During the Screening Visit, spirometry assessments may be performed pre- or postbronchodilators. At all other visits (including the Clinic Visit on Day -23 to Day -10), all spirometry assessments should be performed prebronchodilator. During the Treatment Period, spirometry assessments must be performed before administration of study drug.

In the event that a subject forgets to withhold bronchodilator(s), spirometry should be performed according to the following:

- If a subject's Clinic Visit Day -23 to -10 spirometry is prebronchodilator, but, on a subsequent visit, the subject forgets to withhold bronchodilator use, a postbronchodilator spirometry will be obtained for that visit only, and the visit will not be rescheduled.
- If, on Clinic Visit Day -23 to -10, the subject forgets to withhold his/her dose of bronchodilator, then spirometry and MCC should be performed post-bronchodilator, and all subsequent spirometric measurements (according to the schedule of assessments detailed in [Table 3-2](#)), and the MCC assessment at Day 28, should be performed post-bronchodilator.
- Each spirometry assessment will be recorded in the source documents as prebronchodilator or postbronchodilator.

If more than 1 spirometry assessment is required at a visit, bronchodilators will be withheld until completion of the last scheduled spirometry assessment is completed.

All sites will be provided with spirometers to be used for all study assessments. Spirometry data will be transmitted to a centralized spirometry service for quality review.

Subjects should not be informed of their study-related spirometry results during the Treatment Period.

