11.4.2 Mucociliary Clearance

MCC will be assessed as indicated in [Table 3-1](#) and [Table 3-2](#).

All bronchodilators usage is restricted for 12 hours before the MCC assessments at the Day -23 to Day -10 Visit and the Day 28 Visit.

On Day 28, MCC will occur after the dose of study drug. MCC assessments will be performed according to an SOP in the Study Manual.

Subjects with less than 30 percent predicted FEV₁ on day of MCC, or with acute upper or lower respiratory infection, pulmonary exacerbation, or changes in therapy (including antibiotics) for pulmonary disease within 14 days before scheduled MCC procedures, should not have the assessment performed.

Sites that perform MCC assessments will be expected to procure the MCC equipment as described in the SOP. During the MCC assessment, a series of images will be collected immediately following inhalation of a radiolabeled aerosol and again approximately 6 hours later. Specific instructions for the conduct of MCC testing and submission of results to the central reading center are provided in the Study Reference Manual.

Subjects will not be informed of their MCC results.

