12.3.1 General Considerations

Continuous variables will be summarized using the following descriptive summary statistics: the number of subjects (n), mean, standard deviation (SD), standard error (SE), median, minimum value (min), and maximum value (max). The precision of the measurement for each continuous variable will be specified in the SAP. Unless otherwise specified, minimum and maximum values will be reported with the same precision as the units of the raw data. The mean and median will be reported to 1 additional decimal place, and the SD and SE will be reported to 2 additional decimal places. Any values that require a transformation to standard units (metric or International System [SI]) will be converted with the appropriate precision.

Categorical variables will be summarized using counts and percentages. Percentages will be presented to 1 decimal place.

Baseline value, unless otherwise specified, will be defined as the most recent non-missing measurement (scheduled or unscheduled) collected before the first dose of study drug. For ECG, the baseline will be defined as the average of the most recent triplicate pretreatment measurements before the first dose of study drug.

Change (absolute change) from baseline will be calculated as postbaseline value – baseline value.

Relative change from baseline will be calculated as (postbaseline value – baseline value)/baseline value.

The treatment-emergent (TE) period will include the time from the first dose to the Safety Follow-up Visit or 28 days after the last dose of the study drug for subjects who did not complete the Safety Follow-up Visit.

Rules for handling missing data will be described in the SAP.

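### Day 28 ppFEV1 is taken inside the MCC-day withholding window but its default Day 1 baseline is not, so test conditions can differ for hypertonic saline, dornase alfa and short-acting bronchodilators

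*Protocol*

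**What the plan says.** - **MCC-day restriction.** Protocol Section 9.3, Table 9-1: "No hypertonic saline, bronchodilator, or dornase alfa usage", timed as "12 hours before MCC procedures". The spirometry footnote to Table 3-2 repeats the bronchodilator part: "At the Day 28 Visit, bronchodilator usage is restricted for 12 hours before the MCC assessment".
- **Day 28 order.** The same footnote says that, if the visit is split over two days, "spirometry should be performed on the same day as and preceding the MCC assessment". Section 8.1.2 ties spirometry to the MCC day in the same way. Spirometry is predose, whereas Section 11.4.2 states: "On Day 28, MCC will occur after the dose of study drug".
- **Day 1.** Table 3-2 schedules predose spirometry but no MCC. The test should be prebronchodilator, which Section 11.4.1 defines for short-acting agents as having "withheld their short-acting bronchodilators (e.g., albuterol) or anticholinergic (e.g., Atrovent) for more than 4 hours before the spirometry assessment". Twice-daily-type long-acting agents are withheld for more than 12 hours and once-daily agents for more than 24 hours. Hypertonic saline and dornase alfa are not mentioned.
- **Baseline.** Section 12.3.1 takes the "most recent non-missing measurement (scheduled or unscheduled) collected before the first dose of study drug", with room for exceptions specified elsewhere. The protocol states none for ppFEV1.
- **Analysis.** Section 12.4.1 tests the active group's mean change with a two-sided paired t-test at 0.05. The placebo group is described only.

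**The concern.** A change-from-baseline endpoint assumes that the two measurements were made under the same conditions. Here a subject who follows every rule may inhale hypertonic saline and dornase alfa on the morning of the Day 1 test, and must not do so before the Day 28 test. Section 9.4 asks for a stable CF regimen from at least 28 days before Day 1, so users are expected to be on these therapies at both visits.

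Any effect of one morning's withholding on FEV1 enters the tested mean directly. The test is within the active group, so the placebo group does not subtract it. At the target size there are only 7 placebo subjects, who give a weak descriptive check.

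The protocol accepts the principle of matching. Section 11.4.1 says that if a subject forgets to withhold a bronchodilator at the Day -23 to -10 visit, all later spirometry should also be post-bronchodilator. It has no such provision for hypertonic saline or dornase alfa, and the baseline rule replaces the spirometry from that visit with the Day 1 value.

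**Working it through.** **1. Conditions side by side.** Let g be the hours from Day 28 spirometry to MCC. Spirometry is predose and MCC follows the dose, so g > 0. The minimum time withheld before spirometry is:

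| Agent | Day -23 to -10 | Day 1 (default baseline) | Day 28 |
|---|---|---|---|
| Hypertonic saline, dornase alfa | 12 h less the gap to MCC | no limit | 12 - g h |
| Short-acting bronchodilator | 12 h less the gap to MCC, and >4 h | >4 h | 12 - g h, and >4 h |
| Long-acting bronchodilator | >12 h | >12 h | >12 h |
| Once-daily long-acting | >24 h | >24 h | >24 h |

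Day 1 and Day 28 differ in the first two rows only. The Day -23 to -10 test follows the same pattern as Day 28, because Table 3-1 and Section 8.1.1 also put it on the MCC day and before MCC.

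**2. The plan's own power.** Inputs from Section 12.1 and Table 12-1: change 4.5 points, expected SD 7, two-sided alpha 0.05, 36 active subjects (28 at the target size). Power is that of a paired t-test from the noncentral t distribution with n - 1 degrees of freedom and noncentrality (change / SD) x sqrt(n).

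- n = 36: 4.5/7 x 6 = 3.86, power 96.3% (stated 96%).
- 10% missing: n = 32 gives 94.1% and n = 33 gives 94.7% (stated 95%).
- n needed for 80% power: 21 (stated 21).
- n = 28: 4.5/7 x 5.29 = 3.40, power 90.6% (stated as at least 80%).

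The stated figures reproduce. The issue is measurement conditions, not a wrong number.

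**3. Illustration of a shift.** Assumption, not from the documents: unequal conditions lower the group-mean Day 28 value by b points, averaged over users and non-users, with the SD unchanged at 7. The expected change is then 4.5 - b.

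| b | Expected change | b / 4.5 | Power, n = 36 | Power, n = 28 |
|---|---|---|---|---|
| 0 | 4.5 | 0% | 96.3% | 90.6% |
| 0.5 | 4.0 | 11% | 91.5% | 83.0% |
| 1.0 | 3.5 | 22% | 83.1% | 72.3% |
| 1.5 | 3.0 | 33% | 70.6% | 59.0% |

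The sign of b is also unknown. A shift the other way would inflate the observed change. With no drug effect and n = 36, a shift of 0.5 or 1.0 points in either direction would make the test reject in 7.0% or 13.3% of trials instead of 5%.

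**The case against.** Several points on the other side stand, and they set the limits of the finding.

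- **Bronchodilators in general.** A reader of Table 9-1 might infer that all bronchodilators are mismatched. They are not: long-acting and once-daily agents are under the same Section 11.4.1 limits at both visits.
- **Every user.** A reader might infer that each compliant user is affected. Day 1 permits morning use but does not require it. A subject who takes these agents later in the day, or after the visit, has no mismatch.
- **A known bias against the drug.** It is natural to suppose that withholding lowers FEV1 and so hides part of a true gain. The protocol gives no usage rate, no effect size and no direction for missing one morning's treatment. Zero is a possible value.
- **A broken comparison with MCC.** Section 12.4.1 tests each key endpoint separately, and the readable text has no analysis that compares ppFEV1 with MCC.
- **Other documents.** The baseline definition allows exceptions, so the SAP may name a different ppFEV1 baseline. Detailed MCC instructions are left to the Study Reference Manual.
- **Stakes.** Section 12 calls the study exploratory, without type I error control. At a shift of 0.5 points, power with 28 active subjects is still 83%, above the 80% that the plan claims.

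These points narrow the scope and leave the size open. They do not remove the mismatch that the protocol's own rules permit. An SAP could choose another baseline, but it cannot restore matched conditions to a Day 1 test already done.

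**Conclusion.** The point holds in a limited form. As written, the protocol allows baseline and Day 28 ppFEV1 to be measured under different withholding conditions for hypertonic saline, dornase alfa and short-acting bronchodilators. It affects only subjects who would use these agents in the hours before Day 1 spirometry. The tested quantity is a within-group change, so the placebo group does not correct it.

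The size and direction cannot be derived from the documents. The range of 91% down to 59% power at 28 active subjects rests entirely on an assumed group-mean shift of 0 to -1.5 points with SD 7. It shows sensitivity and is not an estimate. The documents do not support a claim that the ppFEV1 result will be biased by a given amount, or that the stated power is wrong. This is a cheap improvement to a key endpoint of an exploratory study, because pretreatment spirometry under the MCC-day restrictions is already collected.

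**What to change.** 1. Reconcile Table 9-1, the spirometry footnote to Table 3-2, Section 11.4.1 and the baseline definition in Section 12.3.1, so that baseline and Day 28 ppFEV1 are measured under the same withholding conditions. Which withholding rule applies is for the sponsor to decide. The reconciled text should say whether the time is counted back from spirometry or from MCC, since on Day 28 the two differ.
2. Prespecify a sensitivity analysis of the change in ppFEV1 to Day 28 that uses the Day -23 to -10 spirometry as baseline, with the same paired t-test and 95% CI.

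The cost is a text edit and one extra analysis on data already planned. The drawback is a baseline taken 10 to 23 days before the first dose. It may be older where the screening window is extended by 2 weeks (Section 8.1.1.3), or where a subject is rescreened without repeating that visit (Section 8.1.1.2).

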9.3.1 Additional Dietary Restrictions/Prohibited Medications

Prohibited medications and certain foods are not allowed in this study (Screening Period through Safety Follow-up Visit) ([Table 9-2](#)). Known CYP3A4 inducers and inhibitors are restricted because VX-661 and IVA are metabolized at least in part via the hepatic enzymatic pathway using CYP3A4.

A nonexhaustive list of study prohibitions and cautions for food and medication will be provided in the Study Reference Manual.

Table 9-2 Additional Study Restrictions

Restricted Medication/Food	Study Period	
	Screening Period	Treatment Period Through Safety Follow-up Visit
Certain fruits and fruit juices (grapefruit, grapefruit juice, Seville oranges, marmalade)	None allowed within 14 days before the first dose of the study drug	None allowed through the Safety Follow-up Visit
Moderate and strong CYP3A inducers	None allowed within 14 days before the first dose of the study drug	None allowed through the Safety Follow-up Visit
Moderate and strong CYP3A inhibitors (except for ciprofloxacin)	None allowed within 14 days before the first dose of the study drug	None allowed through the Safety Follow-up Visit
Commercially available CFTR-modulators (e.g., Kalydeco, lumacaftor)	None allowed during Screening Period	None allowed through the Safety Follow-up Visit

CYP: cytochrome P450; IVA: ivacaftor.

Note: The use of restricted medication by subjects with medical needs will be addressed on a case-by-case basis with the medical monitor.

9.4 Prior and Concomitant Medications

Information regarding all prior and concomitant medications, including the subject's CF medications, other medications, and herbal and naturopathic remedies administered from at least 28 days before the Screening Period through the Safety Follow-up Visit, if applicable, will be recorded in each subject's source documents. For subjects who are screened but are not subsequently randomized into the study, details of prior medication will only be documented in the subjects' source documents.

- Subjects must remain on a stable medication (and supplement) regimen for their CF from at least 28 days before Day 1 through the Safety Follow-up Visit. Stable medication regimen is defined as the current medication regimen for CF that subjects have been following for at least 28 days before Day 1. Guidelines for stable medication regimens for CF are as follows:
 - Subjects who are taking daily inhaled tobramycin or other chronically inhaled antibiotics should remain on that regimen throughout the study.
 - Subjects who alternate 2 different antibiotics monthly should remain on the same schedule during the study. The timing of the first dose of study drug should be synchronized as closely as possible to the first Day of 1 of the inhaled alternating antibiotics.
- Subjects may receive doses of prednisone of up to 10 mg/day (chronically) or prednisone 60 mg qd for up to 5 days without prior approval of the medical monitor.
- Information about bronchodilator use during the study will be collected and documented. Subjects who are using a bronchodilator must have their spirometry and MCC assessments performed according to the guidelines provided in [Section 11.4.1](#). and [Section 11.4.2](#).
- Concomitant use of medications known to prolong the QT interval should be used with caution during the study, as the effect of VX-661/IVA combination therapy on the QT interval has not been evaluated in a thorough QT study. Consideration should be given to

obtaining an ECG when concomitant medication known to prolong the QT interval is administered.

9.5 Removal of Subjects

Subjects may withdraw from the study at any time at their own request. Subjects may be withdrawn from study drug treatment at any time at the discretion of the investigator or Vertex for safety, behavior, noncompliance with study procedures, or administrative reasons. If a subject has been withdrawn from study drug treatment, the subject should continue to be followed, provided the subject has not withdrawn consent. Subjects will be continued to be followed for safety for 28 days \pm 7 days after the last dose of study drug (see [Table 3-2](#)).

If a subject does not return for a scheduled visit, reasonable effort will be made to contact the subject. In any circumstance, reasonable effort will be made to document subject outcome. The investigator will inquire about the reason for withdrawal, request that the subject return all unused investigational product(s), request that the subject return for a Safety Follow-up Visit, if applicable ([Section 8.1.4](#)), and follow up with the subject regarding any unresolved AEs.

If the subject withdraws consent, no further evaluations will be performed and no additional data will be collected. Vertex may retain and continue to use any data collected before such withdrawal of consent.

The investigator should inquire about the reason for withdrawal of consent.

Subjects must return all unused study drug.

A subject will be withdrawn from study drug treatment for any of the following reasons:

- A female subject or a female partner of a male subject has a confirmed pregnancy.
- A subject's treatment is unblinded by the investigator.

A subject may be withdrawn from study drug treatment after a discussion between the investigator and the medical monitor for any of the following reasons:

- A subject develops a medical condition that requires prolonged concomitant therapy with a prohibited medication or prolonged interruption of the study drug.
- A subject develops a life-threatening AE or a serious AE (SAE) that places him/her at immediate risk, and discontinuation of study drug treatment and withdrawal from the study are deemed necessary.
- A subject is noncompliant with study requirements.
- A subject has an increase in transaminases (ALT or AST) according to evaluations and management described in [Section 11.7.8](#).
- A subject has an increase in QTc according to evaluations and management described in [Section 11.7.4.1](#).
- A subject develops a cataract or lens opacity.

Subjects who discontinue study treatment early should complete the assessments of the ETT and/or Safety Follow-up Visit, as noted in [Section 8.1.4](#).

Subjects who are randomized and whose screening *CFTR* genotype results do not confirm study eligibility must be discontinued from study drug treatment, will undergo ETT and/or Safety Follow-up Visits per [Section 8.1.3](#) and [Section 8.1.4](#), and will then be discontinued from the study. After discontinuation of study drug treatment, these subjects will not undergo any further assessments other than those performed at the ETT and/or Safety Follow-up Visits.

